3.1.1 Description of Baseline Variables

A number of characteristics will be reported for each enrolled subject at time of enrollment. The variables collected will include demographics, medical history, NYHA classification, and cardiovascular medications. Tables and descriptive statistics will be used to summarize subject data with respect to these variables.

3.1.2 Special Considerations

Medtronic statisticians will perform the statistical analyses. Sample size estimates were calculated using SAS Version 9.2 (SAS Institute Inc.).

Analysis Cohort

Patients with any of the following deviations from the study protocol will be excluded from all statistical analysis, as if they were never enrolled in the study:

- Patients that violate any of the inclusion/exclusion criteria.

- Primary prevention patients that did not have LVEF measured at baseline or the 1.5 criteria assessment
- Patients with LVEF measured prior to 40 days post-MI OR prior to 90 days post-MI with revascularization.
- Primary ICD indication patient that is not Class I.
- Primary prevention patients without history of any 1.5 criteria and no Holter test performed
- Primary prevention patients without history of any 1.5 criteria and Holter test performed more than 12 months prior to enrollment or more than 3 months after enrollment.
- Primary prevention patients with no 1.5 criteria assessment.
- Patients with a Baseline or Medical History CRF dated after implant.
- Patients with consent date after implant decision date.
- Patients with previous ICD or CRT-D.
- Patients implanted with a Non-Medtronic device.
- Patients exiting the study or dying prior to completing the Medical History CRF, or the Implant CRF.

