Both primary and secondary prevention subjects will be included in the study. Primary prevention subjects will be further divided into two groups, depending on whether or not they meet the 1.5 prevention criteria described above in Section 1.1. In each of these groups, there are two non-randomized arms: subjects who receive an implant, and subjects who do not receive an implant. Therefore, there are a total of six arms in the study (labeled A-F), described above in Figure 1. The primary analysis focuses on comparing arms A (secondary prevention subjects who receive an implant) and C (1.5 prevention subjects who receive an implant) for time to appropriately treated ventricular tachycardia/ventricular fibrillation (VT/VF). In order to compare arms and adjudicate VT/VF, Medtronic devices must be used.

Subjects who receive an implant of a non-Medtronic ICD/CRT-D should be exited from the study following implant, as this will impact the ability to determine the appropriateness of ICD/CRT-D therapies.

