6.12 Study Exit

A Study Exit eCRF is required when living subjects exit the study. Following exit, subjects will continue to receive standard medical care by their treating physician. All data available through the time of the subject's exit will be used for analysis.

Subjects must be urged to remain in the study as long as possible but may be exited from the study for any of the following situations:

- Subject does not meet inclusion/exclusion criteria
- Subject is implanted with a non-Medtronic device
- Subject lost to follow-up
- Subject chooses to withdraw
- Investigator deems withdrawal necessary (e.g., medically justified, failure of subject to maintain adequate study compliance)

The following information is required to be collected at study exit:

- Date of exit
- Date of last contact (this will be different from date of exit if the subject is lost to follow-up)
- Reason for exit
- Final device interrogation (interrogate all) (if available)

At the end of the study, subjects will not be required to complete an Exit CRF. Instead, a study contact visit form should be completed when subject is notified of closure.

At exit, it is recommended that pre-arrhythmia EGM is programmed to 'off' to save battery life.

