12.3.4 Determination of Patients/Data for Analysis

All subjects in the 1.5 prevention cohort at the time of enrollment will be included.

Version 1

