proc mianalyze parms(classvar=ClassVal) = coxReg_fcs;
class SEXCHAR CMYISCH LBBB NYHA0 DIABETES CRIT15SYNC CRIT15NSVT CRIT15PVC
GROUP;
modeleffects AGE SEXCHAR QRS CMYISCH LBBB NYHA0 DIABETES LVEF0 CRIT15SYNC
CRIT15NSVT CRIT15PVC GROUP ;
run;

```

Kaplan-Meier estimates of the survival curves will be displayed for each group.

The same analysis will be performed comparing implanted and not implanted 1.0 subjects.

Time to Event Considerations

- Time 0 is the enrollment date and subjects will be censored on the last date they were confirmed to be alive.
- Non-implanted patients that later decided to implant the ICD/CRT-D, will have their time to event censored at the day of the implant procedure.
- Implanted patients that explanted the device (without replacement) will continue to be followed as part of the implanted group. These cases will be rare, and unless the explant is completely voluntary (i.e., not due to infection, or imminent subject end-of-life), censoring subjects at explant would bias the results in favor of implant. This is an intention-to-treat approach.
- Patients that had heart transplant will have their time to event censored at the day of the transplant.

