3.3.2 Determination of Patients/Data for Analysis

All subjects in the 1.5 prevention cohort at the time of enrollment who do not meet the criteria in section 3.1.2 of this document will be included. The same criteria apply for the 1.0 subjects in their mortality analysis.

Hypothesis

Although this is an exploratory objective and is not powered, a hypothesis test will be done and compared to an alpha level of 0.05.

H_0 : Hazard ratio of patients with Chagas disease to patients without Chagas disease = 1
 H_a : Hazard ratio of patients with Chagas disease to patients without Chagas disease \neq 1

Only subjects with implant (regardless the prevention criteria group) will be included in the analysis. Subjects with missing information regarding Chagas disease will not be included.

The hypothesis will be tested separately for 1.0, 1.5, and secondary groups.

Analysis Methods

A Cox proportional hazard model will be used to compare the hazard rates of first appropriate VT/VF therapy between subjects with Chagas disease and subjects without Chagas disease within each group (1.0, 1.5, and secondary). The Cox proportional hazards model will only include the Chagas disease indicator. The null hypothesis will be rejected if the p-value for the Chagas disease indicator covariate is less than 0.05.

The analysis will be performed using SAS code similar to:

```
proc phreg data=alldataneeded ;
  class chagas;
  model firstVTVFappropTreat*event(0) = chagas;
run;
```

Time to Event Considerations

- Time 0 is the implant date and, if no events occur, subjects will be censored on the date of their latest device interrogation. Only spontaneous, appropriately treated VT/VF episodes as adjudicated by the episode review committee will count toward the endpoint.
- VT/VF episodes that cannot be adjudicated (due to not saving full episode data or any other reason) will be ignored. Often, these episodes are followed by episodes that can be adjudicated, and since the endpoint is time to first episode, effects on the results from these events will be minimal. In addition, these should be balanced between the comparison groups.

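### SAP 3.1.2 can be read to delete from day 0 anyone given a non-Medtronic device late in follow-up, while SAP 3.3 censors late implants; the SAP must say which rule governs

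*SAP*

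**What the plan says.** SAP 3.1.2 (Analysis Cohort) lists deviations whose subjects "will be excluded from all statistical analysis, as if they were never enrolled in the study". One item reads "Patients implanted with a Non-Medtronic device". It carries no date limit and is not tied to the first implant decision. SAP 3.3.2 carries the list into the mortality analysis: 1.5 subjects "who do not meet the criteria in section 3.1.2 of this document will be included".

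Three other places point elsewhere:

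- SAP 3.3, Time to Event Considerations: "Non-implanted patients that later decided to implant the ICD/CRT-D, will have their time to event censored at the day of the implant procedure". No manufacturer is named.
- Protocol 6.12, which lists a non-Medtronic implant among the exit reasons: "All data available through the time of the subject's exit will be used for analysis".
- Protocol 12.3.4, on the mortality population: "All subjects in the 1.5 prevention cohort at the time of enrollment will be included".

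Protocol 1.2 sets the exit rule, also without a time limit: "Subjects who receive an implant of a non-Medtronic ICD/CRT-D should be exited from the study following implant". The reason it gives is "as this will impact the ability to determine the appropriateness of ICD/CRT-D therapies".

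Late implants are expected. Protocol 6.10.1 offers refusers repeat ambulatory monitoring at 12 and 24 months and foresees that some will then choose a device. Protocol 6.11 records late implants and replacements on a Device Change form that includes the manufacturer.

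**The concern.** Two refusers followed alive for two years and then implanted could be treated in opposite ways. With a Medtronic device, the subject is censored at implant and contributes two years. With another brand, the literal SAP 3.1.2 rule removes the subject from enrolment onward. Membership of the mortality cohort would then depend on a later event that only survivors can reach. A subject who dies before any such implant stays in and counts as a death.

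The stated reason for the exit is that therapies cannot be adjudicated. That bears on the primary endpoint after the new device is in place. It gives no reason to discard survival time observed before it.

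At stake is the hazard ratio for the secondary objective, non-implanted against implanted 1.5 subjects. The rule also reaches the primary analysis: a group A or C subject whose Medtronic system is replaced by another brand would lose follow-up and any appropriate therapy already adjudicated.

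**Working it through.** **Inputs from the documents.** 3-year mortality of 25.7% without and 18.5% with an ICD (protocol 12.3.3); 4800 enrolled, 40% primary, half of those 1.5, 45% of 1.5 subjects implanted (protocol 12.2.6); the accrual pattern in the SAP appendix program, 2.24 years of enrolment and closure at 4.24 years.

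**Assumption.** The rate of late non-Medtronic implants is not given. I use 1%, 3% and 5% per year.

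**1. The plan's own figures.** 1.5 subjects: 4800 × 0.4 × 0.5 = 960, so 960 × 0.45 = 432 implanted and 528 not (the plan says about 430 and 540). First cell of Table 10 (450 implanted, 550 not, 18% vs 26%): events = 450 × 0.18 + 550 × 0.26 = 224; HR = ln(0.74)/ln(0.82) = 1.517; power = Φ(ln 1.517 × √(224 × 0.45 × 0.55) − 1.96) = 87.4%, against 88% stated. The mortality set-up is reproduced.

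**2. Direction.** Let an arm have D deaths in T person-years, with T counted up to the late implant. Subjects with a late implant are alive at that point and exit afterwards, so they hold T_x person-years and no counted deaths. Censoring gives D/T. Deletion gives D/(T − T_x). The arm's death rate is multiplied by T/(T − T_x), which always exceeds 1.

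**3. Deletion in group D only.** Hazards: −ln(1 − 0.257)/3 = 0.0990 and −ln(1 − 0.185)/3 = 0.0682 per year, true HR 1.452. Expected values for 528 subjects, by simulation:

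| Assumed rate | Deleted (share of group D) | Mean years to late implant | T_x | T | T/(T − T_x) | HR if deleted |
|---|---|---|---|---|---|---|
| 1%/year | 12.7 (2.4%) | 1.37 | 17 | 1258 | 1.014 | 1.47 |
| 3%/year | 36.8 (7.0%) | 1.35 | 50 | 1224 | 1.043 | 1.51 |
| 5%/year | 59.6 (11.3%) | 1.33 | 79 | 1192 | 1.071 | 1.55 |

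Censoring at the late implant returns 1.45 at each rate. This simulation makes late implant independent of death risk.

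**4. Deletion in both arms.** If group C subjects are deleted after a non-Medtronic replacement at the same annual rate, the implanted death rate rises by nearly the same factor and the HR is 1.45 to 1.46 throughout.

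**5. False positives under no effect, group D deletion only.** 430 against 540 subjects, common hazard about 0.10 per year, follow-up uniform over 2 to 4.24 years, unadjusted two-sided log-rank test at 0.05, 2000 simulations per scenario:

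| Share of refusers deleted | Null HR | Type I error |
|---|---|---|
| 2% | 1.01–1.02 | 0.05 |
| 5% | 1.03 | about 0.055 |
| 10% | 1.06–1.07 | 0.08–0.10 |
| 15% | 1.10 | 0.12–0.13 |
| 20% | 1.14–1.15 | about 0.18 |

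Censoring keeps the null HR at 1.00 and the error at 0.044 to 0.053.

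**6. Scale against sampling error.** With about 125 and 74 deaths, SE(log HR) = √(1/125 + 1/74) = 0.147, so a 95% interval around 1.45 is about 1.09 to 1.93. The shifts in step 3 equal 0.09, 0.28 and 0.47 standard errors.

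**The case against.** The best defence is that the SAP already handles this subject. SAP 3.3 has a specific rule for refusers implanted later and names no brand. Many neighbouring items in SAP 3.1.2 concern enrolment, baseline or the initial implant, and protocol 6.9 states the non-Medtronic exit in its section on the initial implant. A reader could take SAP 3.1.2 as covering the initial device and SAP 3.3 any later one. That reading is reasonable and may be what was meant. The text does not secure it: neither SAP 3.1.2 nor protocol 6.12 has a time limit, and SAP 3.3.2 makes the exclusions define the cohort before any censoring rule applies. SAP 3.1.3 also says the SAP may supersede the protocol, so the difference from protocol 6.12 is not an error by itself. The conflict inside the SAP is the stronger ground.

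Three stronger readings are tempting, and the documents do not support them.

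- *The rule favours the ICD.* That holds only if deletion falls mainly on group D. Deleted group C replacements work the other way, and neither rate is given.
- *Most deleted subjects are non-implanted.* By head count they could be initial acceptors of another brand, who exit at once with little follow-up. Assuming 10% to 30% non-Medtronic initial devices and a one-month wait, they lose 4 to 15 person-years. Late crossovers exceed this once about 0.5% to 2% of refusers cross over; with a three-month wait, about 1.6% to 6%.
- *SAP 3.3 censors only Medtronic crossovers.* It contains no such restriction.

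Late non-Medtronic implants may also be rare, since sites are chosen with Medtronic programmers and support (protocol 6.1). That argues for a modest rating and leaves the ambiguity in place.

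**Conclusion.** The point holds as an unresolved conflict of rules. Read literally, SAP 3.1.2 conditions the mortality cohort on a future event and discards only event-free time. Whether that biases the comparison, and which way, depends on rates the documents do not give. With group D deletion alone the effect is negligible at about 2% or fewer crossovers in total and becomes material from about 10%. Equal annual rates in both arms roughly cancel. The calculations rest on exponential survival, no covariates, no attrition other than death, and late implant unrelated to prognosis. The endpoint is secondary, and both documents call it exploratory and unpowered, so this is a correction worth making before analysis and no threat to the study's main conclusion. I have put no figure on the effect on the primary endpoint.

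**What to change.** Change SAP wording only:

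1. In SAP 3.1.2, limit the item to subjects whose initial study implant is a non-Medtronic device.
2. In SAP 3.3, state that censoring at a later implant applies whatever the manufacturer and takes precedence over SAP 3.1.2.
3. Keep group C subjects with a non-Medtronic replacement in the implanted group, censored at last confirmed vital status. This fits the intention-to-treat approach SAP 3.3 already takes to explants.
4. In the primary analysis, censor replaced subjects at the last Medtronic interrogation and keep events already adjudicated. Treat groups A and C alike.
5. Report by arm how many subjects were excluded or censored for this reason.

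This needs no new data, because the Device Change form already records the manufacturer. There are two limits. Censoring at a later implant may itself be informative, since protocol 6.10.1 expects some refusers to reconsider after newly found NSVT or frequent PVCs. Initial non-Medtronic recipients also stay out of the mortality analysis although brand has no bearing on vital status; they exit at once and hold little follow-up, and item 5 makes their number visible. Vital-status calls after exit would be an optional addition and are not needed for this fix.

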3.2 Primary Objective: Appropriate Therapy

The primary objective is to demonstrate that appropriate VT/VF therapy rates (shock and ATP) for subjects meeting 1.5 prevention criteria implanted with a Medtronic device (ICD/CRT-D) are equivalent (within 30%) to rates in subjects meeting secondary prevention criteria.

The primary objective will be evaluated by using post-implant time to first appropriate VT/VF therapy (shock and ATP). More specifically, the following hypothesis will be tested:

Hypothesis

H_0 : Hazard ratio of Implanted 1.5 patients to implanted secondary patients ≤ 0.70
 H_a : Hazard ratio of Implanted 1.5 patients to implanted secondary patients > 0.70

Endpoint Definition

The event of interest for this objective is appropriate VT/VF therapy. To qualify as an event, a VT/VF event observed by the ICD/CRT must be adjudicated to be one of the following by the Episode Review Committee:

- Polymorphic VT/VF
- Monomorphic VT
- Non-sustained VT/VF
- Other VT/VF, specify:

Additionally, the episode must have been treated either by ATP, shock, or both by the device.

Performance Requirement

The null hypothesis will be rejected if the one-sided 95% lower confidence bound of the hazard ratio of implanted 1.5 subjects to implanted secondary prevention subjects is greater than 0.70.

Analysis Methods

A Cox proportional hazard model will be used to compare the hazard rates of first appropriate VT/VF therapy between implanted subjects meeting 1.5 prevention criteria and secondary prevention subjects. Because secondary and 1.5 patients are known to be different in many potential covariates, the Cox proportional hazards model will not include any covariates. The one-sided hypothesis test will be performed by computing a 90% two-tailed confidence interval for the hazard ratio between the groups and using the lower limit of this estimated 90% CI as a rejection boundary of the null hypothesis. In particular, if the 90% CI lower limit is greater than 0.7 then the null hypothesis will be rejected.

The analysis will be performed using SAS code similar to:

```
proc phreg data = alldata;
  where group in ('A','C');
  class group (ref = 'A');
  model time2event*eventStatus(0)= group/ rl alpha = 0.1;
  run;
```

Additionally, Kaplan-Meier estimates of the survival curves will be displayed for each prevention criteria group.

Determination of Patients/Data for Analysis

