- All 1.5 prevention and secondary prevention subjects with an ICD/CRT-D implant and at least one device interrogation available in the database will be included in the primary analysis hypothesis test. This includes subjects implanted with a device after the initial enrollment period. These later implants will be included if they are secondary or 1.5 at the time of implant.
- Time 0 is the implant date and, if no events occur, subjects will be censored on the date of their latest device interrogation.
- VT/VF episodes that cannot be adjudicated (due to not saving full episode data or any other reason) will be ignored. Often, these episodes are followed by episodes that can be adjudicated, and since the endpoint is time to first episode, effects on the results from these events will be minimal. In addition, these should be balanced between the comparison groups.

Sample Size Calculation

The minimum required sample size for this study has been estimated to be 4800 subjects based on the following:

- 60% of enrollments will be secondary prevention and 40% primary prevention
- 50% of primary subjects will be in the 1.5 group
- 57% of secondary subjects will get an ICD (includes CRT-D)
- 45% of 1.5 subjects will get an ICD
- 22% of 1.0 subjects will get an ICD
- Annual attrition (includes exits and deaths) will be 10%
- The study will end two years after the last enrollment
- 4000 patients will take 2 years to enroll with enrollment beginning slowly, and then accelerating to a steady 246 per month
- Expected rates of appropriately treated VT/VF in secondary subjects follow Figure 2, with a higher rate in the first year (22.5%), then a constant rate (11.1%) thereafter
- The hazard ratio of 1.5 to secondary is 0.91

Under the above assumptions and using the hypothesis test stated above, 4800 subjects will have 80% power to reject the null hypothesis. With 4800 enrolled patients, it is expected that approximately 1650 secondary prevention subjects will be implanted, 430 1.5 prevention subjects will be implanted, and 200 1.0 subjects will be implanted.

More details, including the simulation program can be found in the Appendix.

Sample Size Re-estimation

Because most of the assumptions above are based only on investigator opinion, the sample size will be re-estimated during the study using the same simulation methods, but changing the following assumptions using the study data:

- % of enrollments will be secondary prevention

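### The exclusion of subjects whose Baseline or Medical History form is dated after implant acts on the implanted arm only in the mortality comparisons

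*SAP*

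**What the plan says.** SAP 3.1.2 (Analysis Cohort) lists deviations whose subjects "will be excluded from all statistical analysis, as if they were never enrolled in the study". One item is "Patients with a Baseline or Medical History CRF dated after implant". No reason is given for it.

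SAP 3.3.2 carries the list into mortality: subjects in the 1.5 cohort at enrollment "who do not meet the criteria in section 3.1.2 of this document will be included", and the same applies to the 1.0 mortality analysis. SAP 3.3 sets time 0 for mortality at enrollment and compares implanted with non-implanted subjects, adjusting for baseline covariates that include NYHA class, LVEF and QRS duration. Missing covariates are to be multiply imputed, with implant status in the imputation model.

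The protocol's populations are wider. Section 12.3.4 takes the whole 1.5 cohort as it stood at enrollment, and 12.2.5 takes all implanted 1.5 and secondary subjects.

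**The concern.** The condition compares a form date with an implant date. In the mortality analysis, having an implant date is what separates the two arms. Take two 1.5 subjects whose Medical History forms are completed equally late. If one accepted a device and the other refused it, the first can be deleted and the second is kept. Late paperwork then decides who stays in one arm and has no such effect in the other.

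The study is not randomized, so the mortality comparison already rests on covariate adjustment. A filter on one arm adds a source of selection which that adjustment addresses only as far as the listed covariates explain why the deleted subjects differ in risk. The rule also fits poorly with two other parts of SAP 3.3:

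- Explanted subjects are kept in the implanted arm, on intention-to-treat grounds, so as not to favor implant.
- Diabetes was added to the Medical History form during the study and is being collected for subjects already enrolled, so late recording is accepted there.

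**Working it through.** **Step 1. Whom the rule can reach.**

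| Group | Implant date? | Can be deleted? | Comparison |
|---|---|---|---|
| A | yes | yes | primary |
| C | yes | yes | primary; mortality (implanted) |
| D | no | no | mortality (not implanted) |
| E | yes | yes | 1.0 mortality (implanted) |
| F | no | no | 1.0 mortality (not implanted) |

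A subject in D or F who is implanted later does acquire an implant date, but would be caught only if the Baseline or Medical History form were dated after that later implant. Hence the wording that the rule reaches the implanted arm only in practice.

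**Step 2. The plan's own figures.**

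- Primary. Inputs from SAP 3.2 are "60% of enrollments will be secondary prevention and 40% primary prevention"; "50% of primary subjects will be in the 1.5 group"; implant rates of 57% (secondary) and 45% (1.5); an event rate for secondary subjects "with a higher rate in the first year (22.5%), then a constant rate (11.1%) thereafter"; "The hazard ratio of 1.5 to secondary is 0.91"; and 10% annual attrition. The appendix adds 2.24 years of enrollment and 2 years of follow-up. Group sizes are A = 4800 × 0.60 × 0.57 = 1642 and C = 4800 × 0.40 × 0.50 × 0.45 = 432. Re-simulating the appendix program (6000 runs) gives power of 81.6%, against 80.4% stated, and a mean hazard ratio of 0.905, against 0.903.
- Mortality. The Schoenfeld formula with 3-year event proportions gives 87.4, 62.4, 31.8, 92.1 and 83.2% for the 450/550 row, against 88, 63, 32, 93 and 82% stated. Some cells in other rows differ by up to about 3 points.

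**Step 3. Loss of numbers.** With 430 implanted, 540 not implanted, and 3-year mortality of 18.5% and 25.7%, mortality power is 78%. Deleting 5, 10 or 20% of the implanted arm gives 77, 76 or 74%. The lost numbers matter little.

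**Step 4. Selection in mortality.** Let a share s of implanted subjects be deleted, with k times the hazard of those kept. If the true ratio of non-implanted to implanted is 1, the ratio seen is, to first order, (1 − s) + s·k. Both s and k are assumptions.

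| s | k = 0.5 | k = 1 | k = 1.5 | k = 2 |
|---|---|---|---|---|
| 5% | 0.975 | 1.00 | 1.025 | 1.05 |
| 10% | 0.95 | 1.00 | 1.05 | 1.10 |
| 20% | 0.90 | 1.00 | 1.10 | 1.20 |

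For scale, 5-10% of 430 is about 22 to 43 subjects. The SAP's mortality figures imply a ratio of ln(1 − 0.257) / ln(1 − 0.185) = 1.45, with log 0.373. The values 0.95 and 1.10 have logs −0.051 and 0.095, which are about −14% and +26% of that log effect.

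**Step 5. Primary analysis.** The criterion is: "In particular, if the 90% CI lower limit is greater than 0.7 then the null hypothesis will be rejected". If deletion occurs in both groups, the C to A ratio is multiplied by m_A / m_C, where m = (1 − s) + s·k within each group. With equal s and k this is 1. For deletion in A only, the standard error of the log ratio, taken from the simulation (geometric mean ratio 0.9008, power 81.6%), is ln(0.9008/0.70) / (1.645 + 0.901) = 0.099. Holding it fixed, the one-sided error at a true ratio of 0.70 is Φ(ln m / 0.099 − 1.645):

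| s (A only) | k = 0.75 | k = 1 | k = 1.5 | k = 2 |
|---|---|---|---|---|
| 5% | 0.04 | 0.05 | 0.08 | 0.12 |
| 10% | 0.03 | 0.05 | 0.12 | 0.25 |

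The error can move either way, depending on k.

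**The case against.** **The rule has a plausible purpose.** A reader might infer that the exclusion serves no analytic end, since the primary model has no covariates and secondary subjects need no 1.5 testing. The documents do not support that. Protocol 6.6.1 records the primary or secondary label at baseline, and that label separates A from the primary prevention groups. Protocol 12.1 keeps a primary prevention subject in that group even after a later VT/VF episode, so a Baseline form completed after implant could record the wrong status. The boundary is also not fixed by a past arrest or VT alone: syncope of undetermined origin with VT/VF induced at EP study counts as secondary, while unexplained syncope can make a primary prevention subject 1.5. For mortality, NYHA, LVEF and QRS ought to predate the device. These reasons stand, although the SAP does not state them. They justify care over values measured after implant, not deletion of the subject. A form date is not a measurement date, and a late form can hold pre-implant values.

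**The SAP may override the protocol.** SAP 3.1.3 says it does so in places. That permits the departure from Protocol 12.3.4 but does not explain it.

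**The stakes are limited.** Mortality is described as exploratory and not powered, and SAP 3.2 replaces excluded subjects at the sample size re-estimation. Both points stand. Replacement restores numbers but does not undo selection.

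**Conclusion.** The point holds for mortality. By construction, the rule in practice removes subjects from the implanted arm only, in both C versus D and E versus F, against Protocol 12.3.4 and without a stated reason. Its size and direction cannot be determined from the documents. The range of 0.95 to 1.10 for a true ratio of 1 assumes 5-10% deleted, 0.5 to 2 times the hazard of those kept, and no correction by the covariates. If the deleted subjects have the same risk as those kept, there is no bias.

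For the primary analysis the point is weaker. A reader might infer that urgent implants after an arrest or VT would have late forms, so that the rule strips high-risk subjects from A and favors non-inferiority. Nothing in the documents says that secondary implants are urgent, that their forms are late more often, or that such subjects have higher risk. The error of 0.25 in step 5 needs 10% deletion in A alone together with a doubled hazard; at k = 0.75 the error falls below 0.05. Bias arises only if deletion differs between A and C and is related to risk.

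**What to change.** Amend this item of SAP 3.1.2 before analysis.

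- **Mortality (1.5 and 1.0).** Drop the exclusion and keep the subjects. Set to missing only covariate values measured after implant, such as NYHA, LVEF and QRS, and let the multiple imputation in SAP 3.3 fill them.
- **Primary.** Apply one rule to both groups: keep subjects whose classification (secondary indication, or 1.5 criteria) is documented from pre-implant source, and exclude only those for whom it is not. Excluding on a late 1.5 assessment alone would not do. Protocol 6.7 does not require that testing in secondary subjects, so such a rule would delete from C and never from A.
- **Reporting.** Give the primary result with and without the exclusion as SAP 3.1.2 now words it, and tabulate affected subjects by group.

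The cost is one revised SAP item, a few more imputed covariates and a source check for the affected subjects.
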